To assess group differences in the number of weeks of abstinence in the follow-up period (Aim-2a), a Poisson regression model was fit with the total number of weeks of self-reported abstinence in the four-week follow-up period as the dependent variable and treatment, site, and treatment by site interaction as independent variables. We conservatively imputed missing values as non-abstinent, thereby including the total ITT sample. We additionally performed a sensitivity analysis for weeks of abstinence by including the weeks preceding the 9th rTMS-treatment visit and immediate post-visit since these two weeks represent the time following the delivery of a total of 16-sessions of rTMS (a similar dose to early rTMS for depression studies). We calculated the relative risk of having a week of abstinence as a measure of the effect size, along with 95% confidence intervals. We used creatinine-corrected urine cannabinoids to verify self-reported abstinence at follow-up weeks 2 and 4, and calculated the proportion that these two methods were concordant.

To evaluate group differences in the number of days of cannabis use (Aim-2b), we utilized a GLMM with the number of days-per-week of cannabis use as the dependent measure. We included participants in the model who had follow-up data (the completer sample; N=51) and given the apparent divergence in days-per-week of cannabis use in the final two-weeks of the follow-up period, we chose to focus our analysis on that period.

Residual normality was assessed for each of the above models using QQ-plots. We included sex in all models to detect a potential effect, but when no significant effects were found, we excluded sex from the subsequent final models. Apart from craving, this was a pilot trial and not powered a priori to detect statistically significant differences; however, statistically significant *p*-values are noted when observed. When reported, a level of $\alpha = 0.05$ was used (two-tailed), and no adjustments for multiple comparisons were made for this preliminary investigation. Effect sizes at each time point were estimated as Cohens d using means and pooled standard deviations. Statistical analyses were conducted using R software (version 4.2.1, GNU project) and SAS version 9.4 (Cary, NC).

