To date there has been limited work examining the effect of rTMS on aspects of CUD. Drawing from the published literature suggesting that excitatory rTMS applied to the DLPFC can reduce craving, the candidate and mentorship team recently completed a preliminary sham-controlled crossover study in cannabis use disordered individuals. The trial suggested that rTMS is safe and well-tolerated, and that a single session of rTMS *acutely* decreases cannabis cue-induced craving. The promising results from our single session trial parallel the single session results found in nicotine and cocaine use disordered populations which subsequently translated into positive multiple session clinical trials(8, 9). As such, it follows that a trial utilizing multiple sessions of rTMS in cannabis use disordered patients may yield positive results.

The overarching goal of this proposal is to investigate if a course of excitatory DLPFC rTMS results in reduced cannabis cue-induced craving in treatment seeking individuals with CUD (Aim1). Additionally, we seek to explore the mechanistic underpinnings of any observed effect by collecting functional magnetic resonance imaging (fMRI) data during cannabis cue-administration before and after the treatment course (Aim 2). These aims will be addressed through a double-blind, randomized, sham-controlled study in which 72 treatment seeking cannabis use disordered participants (36/group) will be given 20 sessions of either *Active* or *Sham* excitatory rTMS applied to the DLPFC. rTMS will be delivered in an accelerated fashion as quickly as in two-weeks, but most often over five-weeks (2 sessions each day, 10 treatment-days). rTMS will be applied in conjunction with a validated three-session Motivational Enhancement Therapy (MET) behavioral intervention.

Aim 1: Determine if a course of excitatory rTMS applied to the DLPFC results in reduced cue-induced craving. We hypothesize that as compared to participants receiving sham rTMS, participants receiving active rTMS will have a reduced level of cannabis cue-induced craving following their final rTMS session as compared to prior to their first rTMS session. We will measure self-reported cannabis craving during a validated cannabis cue-reactivity paradigm, and define cue-induced craving as change in self-reported craving from pre-to-post cue administration.

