Statistical Analysis: Baseline demographic and clinical measures will be compared across treatment groups using standard statistical methods (i.e., categorical variables compared using Pearson chi square test of independence; continuous variables compared using univariate ANOVAs). Characteristics that display imbalance at the baseline measure, association with the dependent variable, or are known to be predictive of cue induced craving, reactivity, or cannabis-use outcomes will be assessed for inclusion as covariates in the final models. To test our primary hypothesis that a full course of active excitatory rTMS will reduce cue induced craving as compared to sham rTMS (Aim 1), generalized linear mixed effects models will be constructed to estimate treatment group differences in craving scores. Overall statistical significance for the effects of treatment group, time, and their interaction will be assessed using a likelihood ratio test that compares the final model, to a model consisting of an intercept term alone. The hypothesis that those receiving active rTMS will have decreased craving will be tested using model-based estimates to construct group level comparisons across all the planned time points. Normality of residuals will be tested for these models and when found in error, appropriate transformations or non-parametric methods will be conducted. For Aim 2 (evaluating the impact of rTMS on cannabis CR), BOLD response during the cannabis cue vs. neutral cue trials will be the primary contrast of interest to test hypotheses. Where significant differences are observed, parameter estimates from task-based models, from each ROI will be extracted and relations with clinical endpoints examined. For our exploratory Aim: The primary analysis will involve preliminarily investigating the efficacy of active rTMS, compared to sham rTMS in increasing the proportion of cannabis abstinent participants during the final two weeks of study treatment (four-week follow-up). A combination of self-reported abstinence from

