Sample Size Justification: The primary focus of this study is to show evidence, with sufficient strength, that treatment with active rTMS will result in decreased cue induced craving (Aim 1), and decreased BOLD response in reward network structures during a cue-reactivity fMRI paradigm (Aim 2) in CUD participants treated with either active or sham rTMS. For Aim 1: Within subject craving measures tend to be highly correlated when measured closely in time and thus we assume a conservative ICC of $p=0.75$ (previous CUD studies range $p=0.60-0.75$) with a standard deviation of ≈ 12.2 . We intend to detect a clinically meaningful craving score difference between the two treatment groups of 8.5 (Cohen's $d=8.5/12.2\approx 0.7$). This is a conservative estimate given that recent multi-session rTMS treatment trials have yielded larger effect sizes on craving ($d=0.98$ (7) in alcohol users, and $d=0.84$ (9) in cocaine users). In the proposed study we will measure increased craving (via MCQ total score) following the presentation of a validated cannabis cue paradigm both before and after a treatment course of rTMS. Under the assumption of independent observations, a total sample size of 32 participants equally allocated to each treatment assignments will provide 80% power with a type 1 error rate of 5% to detect the stated effect size of 0.7. However, the effective sample size in a repeated measures data setting is reduced when assuming an ICC of 0.75. The number of participants per group required is therefore estimated to be $n=27$. Additionally, we need to adjust for study attrition between randomization and the 4-week follow up visit. Assuming an attrition rate of up to 25%, a sample size of **36 participants randomized to each treatment group (n=72 total)** will provide adequate power to detect the primary aim effect size of $d=0.7$ between those receiving active and sham rTMS. **For Aim 2:** In a within subjects investigation of nicotine use disordered participants undergoing a single session of rTMS, there was a significant effect on BOLD response to smoking cues (see figure 2, Preliminary Studies section). If we assume that, as with previous study of cue induced BOLD reactivity in smokers using rTMS, our effects are of medium to large size (e.g. $d=0.7-0.8$) with alpha =5% (2-tailed), a sample of **36 randomized participants in each group will result in greater than 80% power for detecting effects of treatment on CR-BOLD response**. In sum, we are confident that the proposed randomized sample size of 72 participants will be sufficient to test Aims 1 and 2. **For our exploratory Aim**, our recent, non-contingency management based medication trials for cannabis cessation have shown varying placebo abstinence rates (defined as ≤ 50 ng/ml THCCOOH UCT) at the end of study (EOS) treatment (5-15%) (38, 39, 41). Since we are only hoping to provide preliminary data to power a more definitive study, our sample is not designed to sufficiently answer this question definitively. Despite this fact we will still have power to detect a large effect on abstinence. An rTMS abstinence rate of at least 30% greater than placebo at the end of study treatment under the most conservative conditions, at a 10% placebo abstinence rate, a randomized sample size of 36 participants in each treatment group will provide 80% power with a type 1 error of 5% to detect this difference at the end of this pilot study.

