compensated at the end of each visit, and thus will receive pro-rated compensation as they complete the study.

There will be no additional compensation for those choosing to receive open label treatment following the experiment.

b. Sources of Materials

Assessments:

Data collection:

Schedule of visits and assessments and Data Collection:

	Assessment domain	Screen	Baseline	Final rTMS Visit	2-week F/U	4-week F/U
Screening and Enrollment Eligibility:						
MINI International Neuropsychiatric Interview (MINI) for the DSM-5 (54): Structured interview to determine DSM-5 based psychiatric conditions.	Psychiatric history	X				
Urine Pregnancy Test (bHCG)	Pregnancy status	X				
Hamilton Rating Scale for Depression 24-Item (HRSD₂₄)(55): Clinician administered measure of depressive symptoms.	Depressive symptoms	X		X	X	X
The Cannabis Use Disorder Identification Test-R (CUDIT-R)(56): Validated measure assessing severity of disordered cannabis use.	Severity of Cannabis Use	X				
Cannabis Cue-Induced Craving (Aim 1): Primary outcome: Change in MCQ score during cannabis cue paradigm. Secondary outcome: Average weekly change in MCQ assessed during each TMS treatment session.						
The Marijuana Craving Questionnaire (MCQ) (57): Validated measure of cannabis craving. Collected before and after each cannabis cue exposure.	Provoked Cannabis Craving		X	X	X	X
Activation of Reward Structures (Aim 2): Primary outcome: Percent signal change in BOLD response during cue-reactivity fMRI paradigm.						
Substance Use Outcomes (Exploratory Aim): Primary outcome: Number of participants who are abstinent by TLFB for the last 2 weeks of the study with a ratio of four-week to two-week creatinine corrected urine THCCOOH of <0.5. The THCCOOH ratio is able to accurately predict no new cannabis use (10-12).						
Secondary outcomes: change in a) creatinine corrected cannabis level (ng/ml) and; b) subjective use measured by TLFB (number of days used per week and number of cannabis use sessions per week).						
Time Line Follow Back (TLFB) (58): Calendar-based instrument designed to assess substance use.	Self-Reported Substance Use	X	X	X	X	X
Urine Drug Test with Creatinine Corrected Cannabis Level (Collected on the 1st, 5th and 10th rTMS visit, and at follow-up visits)	Objective Substance use	X	X	X	X	X

Delayed Discounting Task (67): Participants choose between receiving hypothetical money immediately or more money if they wait longer.	Cognitive Control		X	X		

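### Aim 1 is worded as one end-of-treatment contrast but tested at every planned time point without adjustment; if any visit may count, the type I error is about 10–13%, not 5%

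*Combined protocol and SAP*

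**What the plan says.** - **Protocol, section A, Aim 1.** The hypothesis is that participants on active rTMS, compared with sham, "will have a reduced level of cannabis cue-induced craving following their final rTMS session as compared to prior to their first rTMS session". Cue-induced craving is defined there as the change in self-reported craving from before to after the cue.
- **Protocol, section D, rTMS Sessions.** The full cue paradigm is given twice: before the first treatment and after the last.
- **Protocol, section D, Statistical Analysis.** The Aim 1 hypothesis "will be tested using model-based estimates to construct group level comparisons across all the planned time points". No visit is singled out, and no order or adjustment is given. An overall likelihood ratio test compares the final model with an intercept-only model.
- **Protocol, section E, Schedule of visits and assessments.** For Aim 1: "Primary outcome: Change in MCQ score during cannabis cue paradigm", with no visit stated in that line. The MCQ is marked at baseline, the final rTMS visit, and the 2-week and 4-week follow-ups.
- **Protocol, section D, Sample Size Justification.** The Aim 1 sample "will provide 80% power with a type 1 error rate of 5% to detect the stated effect size of 0.7".
- **SAP, Aim-1 paragraph.** Total MCQ-SF score is modelled in two a priori mixed models, one with and one without the treatment-by-site-by-time interaction. Neither the deciding visit nor the deciding model is named.
- **SAP, closing paragraph.** Alpha is 0.05 two-tailed, and "no adjustments for multiple comparisons were made for this preliminary investigation". The same paragraph sets craving apart from the outcomes for which the trial was not powered.

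**The concern.** The aim points to one comparison, while the analysis section tests the same aim with several, and the SAP does not say which governs. Craving is the outcome the trial was sized for, at a stated 5% error rate, and that rate belongs to one test. With three unadjusted between-arm comparisons available, a significant difference at the final visit, at 2 weeks or at 4 weeks could each be reported as support for Aim 1. A reader of the results could not tell from the plan which comparison was meant to answer the question.

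**Working it through.** **1. The plan's own figure.** Inputs from the Sample Size Justification: difference 8.5, SD 12.2, type I error 5%, power 80%, ICC 0.75, attrition 25%. The two-sided level is from the SAP.

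- Per group, independent observations: 2 × (1.960 + 0.842)² / (8.5/12.2)² = 32.3, so 33. The plan gives 32, which has 79.6% power. Read as a total (16 per group), 32 would give about 50% power, so it must be per group.
- Allowing for the ICC: 32 × (1 + 2 × 0.75)/3 = 26.7, so 27. The plan gives 27 but no formula; this factor (the mean of three correlated measures) is inferred.
- Attrition: 27/0.75 = 36 per group, 72 in total, as stated.

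The figure reproduces, with one 5% test assumed throughout.

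**2. Number of tests.** The schedule marks the MCQ at three post-baseline visits, so comparing arms at all of them gives three tests. Weekly MCQ change during treatment is labelled secondary in the schedule and is not counted here.

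**3. Familywise error if any of the three may count.** With no true effect, let Z1, Z2 and Z3 be the three test statistics with common correlation c. The error is 1 − P(all |Z| ≤ 1.96). The plan's ICC range is r = 0.60–0.75. Assuming equal correlation between visits, c depends on the contrast:

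- Scores at each visit: c = r.
- Change from a shared baseline: covariance 1 − r, variance 2(1 − r), so c = 0.5.
- Baseline-adjusted: c = (r − r²)/(1 − r²) = r/(1 + r), which is 0.6/1.6 = 0.375 or 0.75/1.75 = 0.43.

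Results from 3 million multivariate normal draws:

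| Contrast | c | Any false positive, two-sided | Any false result favouring active |
|---|---|---|---|
| Visit scores, r = 0.75 | 0.75 | 10.4% | 5.2% |
| Visit scores, r = 0.60 | 0.60 | 11.8% | 5.9% |
| Change from baseline | 0.50 | 12.5% | 6.3% |
| Baseline-adjusted, r = 0.75 | 0.43 | 13.0% | 6.5% |
| Baseline-adjusted, r = 0.60 | 0.375 | 13.3% | 6.6% |
| One named contrast | – | 5.0% | 2.5% |

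The upper limit with independent tests is 1 − 0.95³ = 14.3%. A separate simulation of t-tests with 27 per arm (40,000 null trials) gave 12.7% for change scores and 10.4–12.1% for visit scores, so small samples do not alter the picture.

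**4. Does the likelihood ratio test act as a gate?** No. Against an intercept-only model, a change over time shared by both arms is enough to make it significant. A 3-degree-of-freedom test of treatment alone, used as a gate, would hold the error at about 3–4% when there is no effect at any visit, but that is not the test described.

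**5. Power with one named contrast.** Take 27 evaluable per group, the plan's 8.5/12.2, and a normal approximation. Power is 73% without baseline adjustment, 89% adjusting for a baseline correlated at 0.60, and 97% at 0.75. Keeping all three visits with Bonferroni (0.05/3 = 0.0167) would need 44 per group unadjusted. With 27 per group and baseline adjustment, its power is 79% (0.60) or 93% (0.75). These figures assume that the plan's SD and correlation apply to the contrast tested.

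**The case against.** The strongest reply is that the protocol does fix a deciding visit. Section A states the contrast, section D dates the full cue paradigm to before the first and after the last treatment, and the sample size text also speaks of measuring craving before and after the course. The primary outcome is defined by that paradigm, so its timing follows. The Follow-up paragraph lists only questions about use and urine tests. Without cues at 2 and 4 weeks, cue-induced change does not exist there and cannot decide Aim 1. The absence of adjustment is also disclosed and called preliminary.

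Much of this stands. A reader might infer that the plan has no deciding visit and therefore carries a 10–13% error rate outright; the documents do not support that, because section A supplies the contrast. A reader might also take the allowance for attrition up to the 4-week visit ("we need to adjust for study attrition between randomization and the 4-week follow up visit") as making that visit a second deciding one for Aim 1. That does not follow, because one randomised sample serves all the aims and the exploratory aim is assessed at 4 weeks.

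What does not go away is the sentence in Statistical Analysis, which makes the plural comparisons the test of this very hypothesis. The schedule marks the MCQ at both follow-ups and describes it as collected around each cue exposure, so the documents leave open whether cues are shown there. The SAP models total MCQ-SF score, which can be compared at follow-up with or without cues, and names no contrast. Disclosing the lack of adjustment does not say which test decides, and the preliminary label sits beside a sentence that sets craving apart.

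**Conclusion.** The point holds in conditional form. The analysis section and the SAP do not carry forward the single contrast in section A. Followed as written, with success at any of three post-baseline visits, they give a familywise two-sided error of about 10–13%, or about 5–6.6% against 2.5% for a false result favouring active rTMS. Either way the error is roughly doubled or somewhat more. If the section A contrast alone decides, the error is 5% and nothing is inflated.

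The size rests on three unadjusted two-sided 0.05 tests, the plan's ICC range of 0.60–0.75, equal correlation between visits, and a comparable craving measure at each visit. For cue-induced change as the protocol defines it, the count of three also requires cues at the follow-up visits. This should be corrected, but it does not undermine the design or the sample size.

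**What to change.** **Protocol, section D, Statistical Analysis.** Replace the sentence on comparisons across time points with wording such as: *Aim 1 is decided by one contrast at two-sided 5%: the active-minus-sham difference in the change in cue-induced MCQ from baseline to the final rTMS visit. Comparisons at the 2- and 4-week follow-ups are secondary, are reported as estimates with 95% confidence intervals, and do not decide Aim 1.*

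**SAP, Aim-1 paragraph.**
- Name the same final-visit treatment-by-time contrast, and state which of the two a priori models it is taken from.
- Reconcile the dependent variable, since the SAP uses total MCQ-SF score and the protocol uses cue-induced change.
- Because the SAP is written in the past tense, state that the contrast comes from Aim 1 of the protocol, so that it is not taken for a choice made after the results.

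**Cost.** No new data or participants: 72 stays, and no Bonferroni penalty is paid. The protocol change is brief. The SAP needs a little more, because naming a visit alone would leave two models and two versions of the outcome. The one real concession is that an effect seen only at follow-up no longer counts as a positive Aim 1 result, although it is still reported.

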Aim 2: Determine if a course of excitatory rTMS applied to the DLPFC reduces cue-reactivity in reward network structures during a validated fMRI paradigm. We hypothesize that as compared to participants receiving sham rTMS, participants receiving active rTMS will have a reduced percent signal change in BOLD response in reward structures during a validated cue-reactivity fMRI paradigm following their final rTMS session as compared to prior to their first rTMS session.

Exploratory Aim: Determine if participants receiving active rTMS have a higher rate of abstinence following treatment as compared to participants receiving sham rTMS. We hypothesize that participants receiving active rTMS will be more likely to be abstinent over the final two-weeks of the study period than participants receiving sham rTMS. We will define abstinence as no self-reported cannabis use over the final two weeks of the study, and a ratio of four week to two-week creatinine corrected urine THCCOOH of < 0.5 (10-12).

B. BACKGROUND AND SIGNIFICANCE

Cannabis Use Disorder (CUD) is a common and escalating problem in the United States. The prevalence of CUD more than doubled between 2001-2002 and 2012-2013 (1). Coinciding with the high prevalence of CUD, there has been a high demand for treatment. According to SAMHSA, in 2014 over one million individuals sought treatment for CUD(2). In recent years it has become increasingly clear that those desiring to quit cannabis are rarely able to do so on their own and suffer from a clear withdrawal syndrome(13). Currently available treatments have low long-term success rates(14-17). There has subsequently been significant interest in the development of new treatment options for those individuals with CUD who desire to stop using.

Repetitive transcranial magnetic stimulation (rTMS) is a non-invasive brain stimulation technique that is able to alter cortical excitability and is FDA-approved to treat Major Depressive Disorder. Magnetic fields pass unimpeded through the scalp, skull and meninges, and can directly excite cortical areas. High frequency rTMS (greater than 5 pulses per second) increases cortical excitability(18). Single sessions of rTMS induce temporary changes; however, multiple sessions can induce more long-term changes.

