Behavioral Platform: We will use the three-session version of Brief Marijuana Dependence Counseling BMDC (51) for our behavioral platform, and will follow the protocol outlined in the manual published by NIDA (52). Briefly, we will generate personalized feedback reports (PFRs) by collecting the following measures: Marijuana Use Summary Sheet, Self-Efficacy Questionnaire, Marijuana Problem Scale, and Reasons for Quitting Questionnaire during the baseline visit. These PFRs are used by the clinician to facilitate discussion in the three MET sessions, which will occur most often at treatment visits 2, 4, and 10, regarding participants' frequency of cannabis use, concerns related to use, possible reasons for changing use, high risk use situations, and short and long-term goals related to reduction of use. To ensure our behavioral platform is delivered with fidelity, we will audio-tape sessions for review and fidelity ratings. The audiotapes will be reviewed and assessed for fidelity utilizing techniques developed in the Motivational Interviewing Assessment: Supervisory Tools for Enhancing Proficiency (MIASEP) manual (53).

[figure not shown]
Follow-up: There will be follow up visits 2-weeks and 4-weeks after treatment completion. Participants will be asked about cannabis use and urine drug tests will be performed.

Open label extension: Those participants not achieving abstinence following the four-week follow-up visit, who are interested, will be offered 20 additional treatments of rTMS in an open label fashion. Treatments will

Figure 4

Figure 5

Use of this paradigm elicits: Robust activation in reward regions including the medial prefrontal cortex and anterior cingulate in cannabis, compared to neutral, stimuli in heavy cannabis users.

be delivered in the same fashion as above, however only active treatment will be given (there will be no possibility of sham treatment). Craving, and other data may be collected in the same fashion as during the primary experiment.

Recruitment and Participant Population:

Recruitment: Participants will be recruited through media advertisements (such as Craigslist and facebook) using trialfacts, a professional study-recruitment agency. Ads will recruit heavy cannabis users who are interested in quitting. Participants will undergo a phone screen to ensure they meet basic eligibility criteria (See included phone screen).

Participant Population:

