marijuana during the final two study weeks (via Timeline Follow-Back) as well as a ratio of the creatinine corrected UCTs at the four week follow-up visit divided by the creatinine corrected UCT from the two week follow-up of <0.5 (used in (10-12)) should be sufficient to assign abstinence (yes/no) and assess the overall treatment effect. Logistic regression models will be used to assess end of study abstinence proportions across treatment assignments. Primary analysis models will be reported both unadjusted and adjusted for significant clinical covariates (determined as associated with abstinence from the baseline analysis as well as known clinical confounders). All statistical analysis will be conducted using SAS/STAT version 9.4 (SAS Institute Inc. 2015. SAS® 9.4 Statements: Reference, Fourth Edition. Cary, NC: SAS Institute Inc.).

Missing Data and Attrition. Missing data in longitudinal studies can be a problematic feature but can be mitigated through study design considerations. In order to minimize missing data and study attrition, study simplification and enhanced communication between study staff and participants will be emphasized. We will make every effort to prevent attrition (e.g., phone/text visit reminders, participation compensation, reinforcing adherence to the study protocol at each visit). In addition, in keeping with the Intent to Treat Principle, we will make every effort to continue assessments for the entire course of randomized treatment, even among those who fail to adhere to randomized assignment or stop participating in the study assigned intervention.

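### The protocol's urine-ratio rule for abstinence does not recognise participants who quit early and are already at or near the assay floor at both follow-up visits

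*Combined protocol and SAP*

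**What the plan says.** The protocol gives the same two-part definition in three places.

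- Section A, Exploratory Aim: "We will define abstinence as no self-reported cannabis use over the final two weeks of the study, and a ratio" of four-week to two-week "creatinine corrected urine THCCOOH of < 0.5 (10-12").
- Section D, Statistical Analysis: Timeline Follow-Back abstinence combined with the four-week corrected level divided by that from the "two week follow-up of <0.5 (used in (10-12)) should be sufficient to assign abstinence (yes/no) and assess the overall treatment effect". Logistic regression then compares the arms.
- Section E, Schedule of visits and assessments, which names the exploratory aim's primary outcome: "Number of participants who are abstinent by TLFB for the last 2 weeks of the study with a ratio of four-week to two-week" creatinine-corrected THCCOOH of less than 0.5.

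Both parts are required. Neither document gives an assay limit, a rule for values below it, or an alternative for someone already clear at the first follow-up visit. The only absolute cut-off is in Sample Size Justification, where it describes earlier trials: "varying placebo abstinence rates (defined as ≤ 50 ng/ml THCCOOH UCT) at the end of study (EOS) treatment (5-15%).

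The SAP of June 2023 takes a different route. Aim-2a models the number of self-reported abstinent weeks by Poisson regression. Urine has a supporting role: "We used creatinine-corrected urine cannabinoids to verify self-reported abstinence at follow-up weeks 2 and 4", with the proportion concordant reported. The SAP names neither the ratio nor any other urine criterion.

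**The concern.** The ratio detects a fall. It is informative while THCCOOH is still being cleared, and the protocol's stated reason for using it is that it predicts no new use. A low ratio therefore supports abstinence. A ratio near 1 does not show use if clearance was already complete at the first specimen.

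A participant who stops early in the course can have nothing left to halve between the two follow-up visits. That person has no use in the final two weeks, so meets the outcome as hypothesised, yet fails its urine limb. The abstinence proportions are then too low and the logistic comparison loses power. Sample Size Justification says these data are meant to help power a more definitive study, so understated rates would carry forward.

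**Working it through.** **Inputs from the documents**
- Threshold: ratio below 0.5.
- Interval between specimens: "There will be follow up visits 2-weeks and 4-weeks after treatment completion", so 14 days (section D, Follow-up).
- Course length: two to five weeks, usually five (section D, rTMS Sessions). Someone who quits on day 1 has been abstinent for 35 + 14 = 49 days at the week-2 visit after a five-week course, or 14 + 14 = 28 days after a two-week course.
- Planning case: 10% versus 40% abstinent, 36 per arm, 5% type 1 error, 80% power (Sample Size Justification).

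**Assumptions, not in the documents**
- First-order decline to a reporting floor L, starting level C0 of 10 to 50 times L, half-life h of 3 to 10 days.

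**1. The plan's own figure.** Fisher's exact test, two-sided 5%, full enumeration, 36 per arm, 10% versus 40%: power 80.0%. The stated 80% is reproduced. (Pooled normal approximation 85.2%; continuity-corrected 77.5%.) The power statement is not at fault.

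**2. Both specimens at the floor.** Ratio = L/L = 1, or 0/0 if below-limit results are stored as zero. If the floor value is entered and then creatinine-corrected, ratio = (L/Cr4)/(L/Cr2) = Cr2/Cr4. It then falls below 0.5 only if the week-4 creatinine is more than twice the week-2 creatinine, so the result reflects urine dilution and not cannabis use.

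**3. Near the floor.** Reported value = max(L, C0 × 2^(−t/h)). The week-4 value cannot be reported below L, so the ratio cannot be below 0.5 once the week-2 value is 2L or less. Days of abstinence at the week-2 visit at which this begins = h × log2(C0/2L):
- C0 = 10L, h = 3: 3 × log2(5) = 7.0 days.
- C0 = 50L, h = 10: 10 × log2(25) = 46.4 days.

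Ratios over the 12 combinations of C0/L = 10, 20, 50 and h = 3, 5, 7, 10 days, for someone who never uses again:

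| Days abstinent at week-2 visit | Range of ratio | Combinations failing the rule |
|---|---|---|
| 0 | 0.04–0.38 | 0 of 12 |
| 7 | 0.10–0.50 | 1 of 12 |
| 14 (quit as treatment ended) | 0.14–1.00 | 4 of 12 |
| 28 | 0.32–1.00 | 9 of 12 |
| 49 (quit at start of a five-week course) | 0.60–1.00 | 12 of 12 |

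The one failure at 7 days is C0 = 10L, h = 3: 10 × 2^(−7/3) = 1.98L, and L/1.98L = 0.504. A worked cell at 28 days: C0 = 20L, h = 7. Week 2 = 20 × 2^(−4) = 1.25L; week 4 = 20 × 2^(−6) = 0.31L, reported as L; ratio = 1/1.25 = 0.80.

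The failure is not universal outside this grid. With C0 = 80L and h = 10, at 49 days: week 2 = 80 × 2^(−4.9) = 2.68L, week 4 = 80 × 2^(−6.3) = 1.02L, ratio 0.38, which passes. Separately, with no floor at all, the ratio is 2^(−14/h), which is 0.50 or more for half-lives of 14 days or longer.

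**4. Effect on the comparison.** Let f be the share of true abstainers the rule misses, taken as equal in both arms. The documents do not give f.

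| f | Observed rates | Fisher power, 36 per arm |
|---|---|---|
| 0 | 10% v 40% | 80.0% |
| 10% | 9% v 36% | 73.5% |
| 25% | 7.5% v 30% | 61.4% |
| 50% | 5% v 20% | 34.5% |

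At f = 25% the risk ratio stays at 4, the risk difference falls from 30 to 22.5 points, and the odds ratio falls from (0.40/0.60)/(0.10/0.90) = 6.0 to (0.30/0.70)/(0.075/0.925) = 5.3. The planning range of 5–15% comes from the 50 ng/ml definition, so 10% need not be the control rate under the ratio rule. The table shows direction and scale only.

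**The case against.** The strongest objection is that the later SAP does not use this rule. Its Aim-2a outcome is self-reported weeks, with missing weeks imputed as non-abstinent, and urine is used only to report concordance. A reader might infer that the SAP's abstinence result is biased toward no effect. The text does not support that: nothing says urine reclassifies anyone. Nor does it show that the ratio governs the verification. The week-4/week-2 ratio cannot verify week 2, which suggests some unstated criterion was used. This part of the objection stands in full.

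A reader might also infer that the rule discards the best responders mainly in the active arm. That needs both a treatment effect and earlier quitting under active treatment, and the documents give no data on either. With equal loss the risk ratio is unchanged, although the odds ratio, risk difference and power fall.

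It is also tempting to count as an error that someone who used until the week-2 visit and then stopped is classed as abstinent. The outcome is abstinence over the final two weeks, so that classification is correct.

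Finally, the aim is exploratory, the protocol says the sample is not designed to settle it, and the half-lives and floors above are assumptions. That limits the weight of the point. It does not remove the gap, because the protocol states the two-part rule three times without an exception for specimens already at the floor.

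**Conclusion.** The concern holds for the protocol's exploratory abstinence outcome. As written, the rule does not class as abstinent a participant who reports no use and is at or near the assay floor at both follow-up visits. A ratio below 0.5 from two floor specimens would arise only from a difference in urine concentration. The effect is to understate abstinence and reduce power for the logistic comparison.

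Its size is unknown. Under the assumed half-lives of 3 to 10 days and starting levels of 10 to 50 times the floor, everyone who quits at the start of a five-week course fails, and no one who quits at the week-2 visit fails. How many participants fall in between, and whether they differ by arm, cannot be derived from the documents.

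The SAP's Poisson analysis is not affected. Its concordance proportion would be affected only if the ratio was the verification rule, in which case early quitters with accurate self-report would count as discordant.

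**What to change.** Define urine-confirmed abstinence as negative self-report AND (ratio below 0.5 OR week-4 specimen at or below a pre-stated limit). The second limb should rest on the week-4 specimen alone. If both specimens had to be at or below the limit, someone just above it at week 2 could still fail both limbs when the week-4 value cannot be reported below half the week-2 value.

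Also state:
- the limit and whether it is raw or creatinine-corrected. The 50 ng/ml in Sample Size Justification is a candidate, but there it describes earlier trials and is not said to be creatinine-corrected;
- how below-limit values enter the ratio;
- the week-2 verification criterion for the SAP: the same limit, or a ratio to the specimen already collected at the tenth rTMS visit. The limit alone could miss recent quitters who are still clearing.

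Report the ratio-only rule as a sensitivity analysis. The SAP is written in the past tense, so label the revised rule as specified after the fact.

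The cost is a few sentences, with no new specimens or assays. The downside is that a low-level user below the limit could pass on urine, which the self-report condition limits. Slow excretors (half-life of 14 days or more) still above the limit at week 4 would still fail.
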